7.5 Diagnostic Efficacy Assessments

7.5.1 Assessment of the Composite Reference Standard

The composite Reference Standard may consist of histopathology, conventional imaging modalities that are routinely used in the diagnosis and staging of PC and PSA levels. ⁶⁴Cu-SAR-bisPSMA scans will not form part of the Reference Standard.

The Reference Standard status will be determined by an independent, blinded, central expert panel. The expert panel will establish the Reference Standard disease status (on a participant-and region-level) for each participant individually, using information provided by the site's Investigator. The experts will be blinded as described in Section 4.3.

The Investigator will be required to submit all relevant clinical evidence available for the participant to enable the assessment of the Reference Standard. Relevant evidence will include:

- All available histopathology reports related to the participants disease history;
- All available conventional scans and related local reports collected as part of Screening (within 60 days of Day 0) and Follow-up (within 180 days [±15 days] of Day 0);
- PSA levels recorded as part of Screening and Follow-up;
- All available PC related symptom and treatment history;

The composite Reference Standard will be hierarchical in nature, with three levels of evidence that will be applied as follows:

- Level 1: Evaluable histopathology from biopsy or surgery OR in case that histopathology is not available, inconclusive or negative:
- Level 2: Conventional imaging procedures OR if neither histopathology or conventional imaging are available or informative:
- Level 3: Confirmed PSA response following radiation or other salvage focal therapy (as long as no concomitant ADT is given), defined as total PSA decline by ≥50% from baseline, confirmed by a second value within four weeks as per the Prostate Cancer Working Group 3 criteria²⁵.

The expert panel will use the collective information to determine and record each region with histopathology demonstrating PC, the number of lesions suspicious for PC detected on conventional imaging in each anatomical subregion and whether the participant achieved confirmed PSA response (if applicable).

Region(s) with no histopathology demonstrating PC or no unequivocal lesion recorded in any of the anatomical subregions on conventional imaging will be deemed negative for the region level Reference Standard status.

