Region(s) with histopathology demonstrating PC will qualify the region as positive for the region level Reference Standard status. A subregion with at least one unequivocal lesion (or

cluster of lesions or diffuse sclerotic metastasis) on conventional imaging will qualify the subregion as positive for the Reference Standard status.

If the expert panel judged that the available information is insufficient to provide a reliable conclusion, the result will be recorded as non-evaluable (e.g., no follow-up assessments were completed) or inconclusive. The reason for selecting a non-evaluable or inconclusive result will be documented.

Further details on the process and interpretation of the conventional imaging will be provided in the Imaging Review Charter.

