7.5.2 Assessment of Reference Standard against the ⁶⁴Cu-SAR-bisPSMA PET/CT Results

For the assessment of the Reference Standard against the ⁶⁴Cu-SAR-bisPSMA PET/CT, region-level matching will be used for histopathology, subregion-level matching for imaging and participant-level matching for PSA response to radiation or other salvage focal therapy (refer to Section 7.5.1). Matching of the Reference Standard against the ⁶⁴Cu-SAR-bisPSMA PET/CT results will be completed via statistical programming.

Assessment of **region-level** Reference Standard against the ⁶⁴Cu-SAR-bisPSMA PET/CT results:

- Histopathology: A region that is ⁶⁴Cu-SAR-bisPSMA PET-positive (i.e., includes at least one unequivocal PET-positive lesion) and Reference Standard positive, will be assigned as true positive (TP) for the region-level status.
- Imaging: A subregion that is ⁶⁴Cu-SAR-bisPSMA PET-positive (i.e., includes at least one unequivocal PET-positive lesion) and Reference Standard positive (i.e., includes at least one unequivocal lesion detected on conventional imaging in that subregion), will be assigned as TP. A region that includes at least one TP subregion will be assigned as TP for the region-level status.
- A region that is ⁶⁴Cu-SAR-bisPSMA PET-positive (i.e., includes at least one unequivocal PET-positive lesion) and is Reference Standard negative based on at least 1 evaluable timepoint, will be assigned as false positive (FP) for the region-level status.
- A region that is ⁶⁴Cu-SAR-bisPSMA PET-negative (i.e., no unequivocal PET-positive lesion or only equivocal lesion(s) detected within the subregions) and Reference Standard negative, will be assigned as true negative (TN) for the region-level status.
- A region that has either non-evaluable ⁶⁴Cu-SAR-bisPSMA result for a specific timepoint or has a non-evaluable or inconclusive Reference Standard will not be assigned for that timepoint.

Assessment of **participant-level** Reference Standard against the ⁶⁴Cu-SAR-bisPSMA PET/CT results:

- A participant with at least one TP region AND/OR at least one unequivocal ⁶⁴Cu-SARbisPSMA PET-positive lesion and confirmed PSA response to radiation or other salvage focal therapy, will be assigned as TP for the participant-level status.
- A participant with at least one unequivocal ⁶⁴Cu-SAR-bisPSMA PET-positive lesion who does not meet the above criteria to be deemed TP, will be assigned as FP for the participant-level status.

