#### • False Positive:

 A region that is Cu-SAR-bisPSMA PET-positive (i.e., includes at least one unequivocal PET-positive lesion) and Reference Standard negative based on at least 1 evaluable timepoint.

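### Protocol 7.5.1 makes a region Reference Standard negative when either form of confirmation is absent; it should require both to be absent, in a region that the reference evidence covered

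*Protocol*

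**What the plan says.** **Hierarchy (Protocol 7.5.1).** The first tier reads "Level 1: Evaluable histopathology from biopsy or surgery OR in case that histopathology is not available, inconclusive or negative", and in those cases conventional imaging applies as Level 2. Confirmed PSA response is Level 3 and is matched at participant level only.

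**Negative (Protocol 7.5.1).** The sentence opens "Region(s) with no histopathology demonstrating PC or no unequivocal lesion recorded in any of" its subregions on conventional imaging, and deems the region negative.

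**Positive (Protocol 7.5.1).** "Region(s) with histopathology demonstrating PC will qualify the region as positive for the region level Reference Standard status". For imaging, one unequivocal lesion makes the *subregion* positive. No sentence in 7.5.1 says that imaging makes the *region* positive.

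**Insufficient evidence (Protocol 7.5.1).** "If the expert panel judged that the available information is insufficient to provide a reliable conclusion, the result will be recorded as non-evaluable", or as inconclusive.

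**Matching (Protocol 7.5.2, SAP 7.8).**
- A PET-positive region with positive histopathology is a true positive (TP).
- For imaging: "A region that includes at least one TP subregion will be assigned as TP for the region-level status".
- A PET-positive region is a false positive (FP) if it is "Reference Standard negative based on at least 1 evaluable timepoint".
- A PET-negative, Reference Standard negative region is a true negative (TN).
- Regions with a non-evaluable or inconclusive Reference Standard are not assigned.

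Protocol 7.5.2 says that matching against the PET/CT "results will be completed via statistical programming". SAP 7.8 uses the negative status without defining it and leaves the full algorithm to a supplement spreadsheet.

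**The concern.** The negative sentence joins its two conditions with *or*, so the absence of either one is enough. That conflicts with the hierarchy just above it, with the positive rules just below it, and with the TP rules in Protocol 7.5.2 and SAP 7.8.

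The status decides which PET-positive regions count as FP, and so it decides region-level PPV on Day 0 and Day 1, two of the four co-primary efficacy endpoints. A participant can be TP through a single TP region, so a region wrongly moved to FP can also lower the participant-level correct detection rate. On the PET-negative side, a region with an unequivocal follow-up lesion but no positive histopathology would literally be TN, although SAP 7.8 has a separate label, Test Negative, for a negative scan with a positive Reference Standard.

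The second issue is coverage. The FP rule asks for one evaluable timepoint but does not say that the evidence must cover the region being judged.

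**Working it through.** **1. The rules side by side.** Take a PET-positive region with at least one evaluable timepoint.

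| Reference evidence | Negative under the literal *or*? | TP rule met? | FP rule met? | Status if *or* becomes *and* |
|---|---|---|---|---|
| Positive histopathology and imaging lesion in the PET subregion | No | Yes | No | TP |
| Positive histopathology, no imaging lesion | Yes | Yes | Yes | TP |
| No positive histopathology, imaging lesion in the PET subregion | Yes | Yes | Yes | TP |
| No positive histopathology, imaging lesion only in another subregion | Yes | No | Yes | Neither |
| Neither source positive | Yes | No | Yes | FP |

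Rows 2 and 3 are the contradiction. Row 4 shows that changing the one word is not enough: such a region would drop out of PPV = TP/(TP + FP), and PPV would rise.

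**2. The plan's own figure (Protocol 10.3, SAP 4.2).** Expected positive regions: 40 × 0.65 × 1.3 = 33.8, taken as 34. The exact 95% lower limit first exceeds 40% at 20 of 34 (limit 0.407; at 19 it is 0.379). With a true PPV of 65%, P(X ≥ 20) = 0.826, which agrees with the stated power above 80%. Reading *and* for *or* leaves this unchanged, because 65% is an input. Expected TP regions: 34 × 0.65 = 22.1.

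**3. If the literal rule overrode TP.** Let *h* be the share of TP regions with positive histopathology. The documents do not give it. Suppose that imaging-only TP regions become FP and histology-positive ones stay TP. Then PPV = 0.65 × *h*, and power is P(X ≥ 20) with n = 34.

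| *h* (assumed) | PPV | Power |
|---|---|---|
| 30% | 0.65 × 0.30 = 19.5% | about 0 |
| 50% | 0.65 × 0.50 = 32.5% | 0.1% |
| 70% | 0.65 × 0.70 = 45.5% | 8.3% |
| 100% | 0.65 × 1.00 = 65% | 82.6% |

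If the override also reached regions confirmed by histopathology alone (row 2), the values would be lower.

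**4. The coverage gap.** Let *u* be the share of PET-positive regions missed by an otherwise evaluable scan, also not given. Assume that these regions would have been confirmed at the same 65% had they been covered.
- Called negative, they become FP and PPV = 0.65 × (1 − *u*). For *u* = 10% this is 58.5% (power 55.8%), and for 20% it is 52.0% (power 26.7%).
- Called non-evaluable, they leave the denominator and PPV stays at 65%. Power is 73.6% with 31 regions (34 × 0.9 = 30.6) and 67.0% with 27 (34 × 0.8 = 27.2).

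**The case against.** **The intent is clear from context.** Imaging is used when histopathology is unavailable, inconclusive or negative, so under the literal *or* Level 2 could never confirm a region. SAP 9.14.3.2 reports region-level PPV for regions resting on imaging without contributing histopathology; on the literal reading every TP in that row would also be FP. This stands as evidence of intent. It does not repair the sentence, which for a region without a biopsy is the only text in 7.5.1 that assigns a region-level status.

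**The algorithm is held elsewhere.** The supplement and the review charters were not available and may already settle the point, so how the matching is programmed cannot be known from these documents. That stands too. A co-primary classification should still not depend on a supplement contradicting the protocol.

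**A reader might infer that PET-positive regions with no reference data become false positives.** The documents do not support that. Insufficient information is non-evaluable or inconclusive (Protocol 7.5.1), and such regions are not assigned (Protocol 7.5.2, SAP 7.8). They are outside the PPV denominator (Protocol 10.4.5.1, SAP 9.14.1), and SAP 7.3 treats missing reference data as non-evaluable. They count as FP only in the worst-case sensitivity analysis. Protocol 7.3.3 also requires follow-up imaging for everyone. What remains is narrower:
- The evaluable timepoint is not tied to the region.
- The only example given of non-evaluable is that no follow-up was completed.
- Follow-up scans follow institutional protocols with no stated field of view.
- Both sensitivity analyses act on missing or non-evaluable data (the worst case also on inconclusive data), so neither would reveal a missed region recorded as negative.

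**A reader might also infer that PPV will collapse.** That needs FP to override explicit TP rules and a low share of histology-confirmed regions. Neither is established. Protocol 7.4 asks for histopathology from at least one PET-positive lesion per region where clinically feasible.

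**No formal hypothesis test is planned (SAP 4.1).** This is correct, so the power figures above describe the planning target and not a decision rule. The PPV estimate is still co-primary.

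**Conclusion.** The concern holds. The only definition of a Reference Standard negative region is wrong as written: a PET-positive region confirmed by just one of the two sources meets both TP and FP, and no precedence is stated. The evident intent is *and*.

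If the program follows that intent, the planned figures do not move. If it follows the sentence, PPV could lie anywhere from about 19.5% to 65% as the histology-confirmed share runs from 30% to 100%. That range rests on an assumed share and on FP overriding TP, so it shows what the ambiguity could cost and is not a forecast.

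The coverage point is a secondary clarification. It concerns regions missed by an otherwise evaluable scan, not regions without reference data, and the documents give no count of them.

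**What to change.** Put the following in Protocol 7.5.1 and 7.5.2 and repeat it in SAP 7.8:

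> A region is Reference Standard negative only if at least one evaluable follow-up reference assessment (scan or histopathology) covers that region, AND no histopathology in it demonstrates PC, AND no unequivocal lesion is recorded in any of its subregions on conventional imaging. A region without such coverage is non-evaluable. TP takes precedence over FP. A PET-positive region with an evaluable Reference Standard that does not meet the TP rule, including one whose imaging lesion lies in a different subregion, is FP.

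The last sentence mirrors the participant-level FP rule already in SAP 7.8 and keeps row 4 of the table in the denominator. Admitting histopathology as coverage lets a region with evaluable negative histopathology but no scan be classified.

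The cost is a wording change in both documents, a check that the analysis supplement agrees, and one coverage field per region on the panel form. SAP section 1.0 already provides for an amendment before database lock. The downside is that a few regions move from FP or TN to non-evaluable, which leaves somewhat fewer regions for PPV.

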10.3 Determination of Sample Size

The co-primary endpoints include participant-level correct detection rate (CDR) or true positive detection rate and region-level positive predictive value (PPV).

The assumed participant-level CDR of ⁶⁴Cu-SAR-bisPSMA PET/CT imaging is 42% in participants with biochemical recurrence of PC. A sample size of 40 participants is estimated to provide more than 85% power to achieve a lower boundary of a 2-sided 95% exact binomial confidence interval (CI) about the estimated CDR that exceeds 20%. Accounting for a 20% non-evaluable rate (including lost to follow-up), approximately 50 participants will need to undergo ⁶⁴Cu-SAR-bisPSMA PET/CT in this study.

For the co-primary efficacy endpoint of region-level PPV, assuming 65% of participants are estimated to have ⁶⁴Cu-SAR-bisPSMA PET/CT positive findings in this target population and each participant with positive findings has an average of 1.3 positive regions, then 40 participants are expected to produce approximately 34 positive regions. The assumed region-level PPV rate of ⁶⁴Cu-SAR-bisPSMA PET/CT imaging is approximately 65% in all PET positive regions. Therefore, a sample size of 40 participants (i.e., approximately 34 positive regions) is estimated to provide more than 80% power to achieve a lower boundary of a 2-sided 95% exact binomial CI about the estimated region-level PPV that exceeds 40%.

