The algorithm for determining the status of a subregion for the Cu-SAR-bisPSMA result on Day 0 or Day 1 was changed during the study based on an amendment to the imaging database for collection of non-evaluable results for subregion-level data. This change occurred on 13-Feb-2023 and participants will be flagged in listings as to whether their Cu-SAR-bisPSMA results were collected before or after this change.

Prior to this amendment, subregion status is defined as the following:

- A subregion is considered Cu-SAR-bisPSMA PET/CT positive if it has at least one unequivocal PET-positive lesion.
- If a subregion has only equivocal lesions or no lesions present, the subregion is considered negative.

After this amendment, subregion status is defined as the following:

- A subregion is considered Cu-SAR-bisPSMA PET/CT positive if it has at least one unequivocal PET-positive lesion.
- If a subregion has only equivocal lesions, the subregion is considered negative.
- If a subregion is marked as non-evaluable, then the subregion is non-evaluable and cannot be used in the comparison with the reference standard, this will be excluded from the analysis for that participant.
- If the subregion is **not** marked as non-evaluable but there are no lesions present, the subregion is considered negative.

A reference datapoint is a follow-up histopathology assessment, PSA response, or imaging scan (with the exception of the Cu-SAR-bisPSMA PET/CT scans) occurring between Day 1 and Day 180 that is used to confirm if PC is demonstrated on a participant, region and subregion level. All reference datapoints on study will be evaluated by the expert reference panel to determine the reference standard for each participant. The results will be indicated as "positive", "negative", "inconclusive/equivocal", or "non-evaluable". Additional details are provided in the Reference Standard Review Panel Charter.

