## • Non-evaluable:

o A region that has either non-evaluable (NE) Cu-SAR-bisPSMA PET/CT results for a specific timepoint (Day 0 or Day 1) or has a non-evaluable or inconclusive Reference Standard will not be assigned for that timepoint.

Assessments of **Participant-Level** Reference Standard against the Cu-SAR-bisPSMA PET/CT results:

• True Positive:

September 4, 2024 CONFIDENTIAL Page 22 of 46

- A participant with at least one TP region and/or at least one unequivocal Cu-SAR-bisPSMA positive lesion in any region and a confirmed PSA response to radiation or other salvage focal therapy.
  - Confirmed PSA response following radiation or other salvage focal therapy (as long as no concomitant ADT is given) = total PSA decline ≥50% from baseline, confirmed by a 2nd value within 4 weeks per Prostate Cancer Working Group 3 criteria.

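### The documents do not settle whether a PET-positive region with only equivocal lesions on reference imaging is a false positive or is left out of co-primary region-level PPV, and Protocol 7.5.1 joins its two conditions for a negative region with an 'or' that should be 'and'.

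*Protocol*

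**What the plan says.** **Protocol 7.5.1.** The negative rule covers regions with no histopathology showing cancer *or* with "no unequivocal lesion recorded in any of the anatomical subregions on conventional imaging will be deemed negative" for the region-level Reference Standard. The next paragraph makes a region positive on histopathology showing cancer, and a subregion positive on at least one unequivocal imaging lesion. It then lets the panel record a non-evaluable or inconclusive result, with a documented reason, when the information is insufficient for a reliable conclusion.

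**Protocol 7.5.2.** A PET-positive region that is Reference Standard negative on at least one evaluable timepoint is a false positive. A region with a non-evaluable or inconclusive Reference Standard is not assigned.

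**SAP 7.7.** On the panel's output: "The results will be indicated as 'positive', 'negative', 'inconclusive/equivocal', or 'non-evaluable". For the ⁶⁴Cu PET scan the SAP says that a subregion with only equivocal lesions is negative. It gives no matching rule for reference imaging.

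**SAP 7.8 and 9.14.1.** A region that "has a non-evaluable or inconclusive Reference Standard will not be assigned for that timepoint". PET-positive regions without an evaluable Reference Standard are excluded from PPV, which is TP/(TP + FP).

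**SAP Table 3** (deviations from protocol analyses) lists nothing on this point.

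**The concern.** Region-level PPV is co-primary at both Day 0 and Day 1. A false positive stays in its denominator and an unassigned region leaves it, so the class given to an equivocal-only region changes the estimate directly. Region-level FPR and the region-level true-negative counts depend on the same class, because each requires a Reference Standard negative region.

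Such regions are foreseeable. Entry requires negative or equivocal conventional imaging (Protocol 4.1.1, criterion 6), follow-up must repeat the baseline modalities (7.3.3), and Visit 6 exists for participants still negative or equivocal at Day 90 (8.1.4). Matching is done by statistical programming (7.5.2), so a programmer needs one rule and literal wording matters.

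**Working it through.** **1. The texts side by side, for a PET-positive region whose reference imaging shows only equivocal lesions and which has no positive histopathology**

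| Source | Class of the region | Effect on PPV |
|---|---|---|
| Protocol 7.5.1 negative rule, then 7.5.2 | Negative, so FP | In the denominator |
| Protocol 7.5.1 panel route, then 7.5.2 | Inconclusive if the panel judges information insufficient | Out |
| SAP 7.7, then 7.8 and 9.14.1 | Inconclusive/equivocal on the natural reading, so unassigned | Out |

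**2. The 'or'**

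Let A = no histopathology showing cancer, and B = no unequivocal lesion on conventional imaging. The sentence reads: negative if A or B.
- Biopsy positive, no unequivocal imaging lesion: B is true, so negative. The next paragraph of 7.5.1 makes it positive.
- Unequivocal imaging lesion, no positive biopsy: A is true, so negative. Protocol 7.5.2 makes it TP if the PET-positive subregion matches.

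Only 'A and B' agrees with the surrounding text.

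**3. The plan's own PPV figure**

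Inputs from Protocol 10.3: "40 participants are expected to produce approximately 34 positive regions" (40 × 0.65 × 1.3 = 33.8), an assumed PPV of 65%, and the target of a "lower boundary of a 2-sided 95% exact binomial CI about the estimated region-level PPV that exceeds 40"%. The smallest count that meets the target is 20 of 34 (Clopper-Pearson lower limit 40.7%). P(X ≥ 20 | n = 34, p = 0.65) = 82.6%, which reproduces the stated power of more than 80%.

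**4. Effect on the estimate**

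Let k be the number of equivocal-only PET-positive regions. The documents do not give k, so 0 to 6 is an assumption. With 22 TP (22/34 is close to the assumed 65%):

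| Treatment | PPV | 95% lower limit |
|---|---|---|
| All k counted as FP | 22/34 = 64.7% | 46.5% |
| k = 2 excluded | 22/32 = 68.8% | 50.0% |
| k = 4 excluded | 22/30 = 73.3% | 54.1% |
| k = 6 excluded | 22/28 = 78.6% | 59.0% |

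With 19 TP, one short of the 20 needed: 19/34 = 55.9%, lower limit 37.9%; 19/32 = 59.4% (k = 2 excluded), lower limit 40.6%; 19/30 = 63.3% (k = 4 excluded), lower limit 43.9%.

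**5. Effect on power**

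The sizing text says that PPV with "PET/CT imaging is approximately 65% in all PET positive regions", but not under which rule. Let q be the equivocal-only share of all PET-positive regions (assumed).
- If 65% holds among 34 assigned regions and equivocal-only regions are then added as FP, n = 34/(1 − q) and PPV = 0.65(1 − q). For q = 5%, 10%, 15%: n = 36, 38, 40; PPV = 61.8%, 58.5%, 55.3%; power = 72.6%, 59.8%, 45.2%.
- If 65% already counts them as FP and they are then excluded, n = 34(1 − q) and PPV = 0.65/(1 − q). For the same q: n = 32, 31, 29; PPV = 68.4%, 72.2%, 76.5%; power = 90.0%, 93.7%, 97.5%.

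These follow the plan's own binomial treatment of regions.

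**The case against.** The best reply is that no contradiction has been shown. The SAP lists four labels for reference datapoints of every kind: histopathology, PSA response and imaging. It never says that a region with only equivocal imaging lesions gets the merged label, and its unassigned rule names non-evaluable and inconclusive, not equivocal. Its one explanation of the word inconclusive concerns histopathology results. The Protocol has the same inconclusive route, so the texts can be read together: equivocal-only is negative by default unless the panel documents insufficient information. The mapping may be fixed in the panel charter, the Imaging Review Charter or the programming supplement, none of which is available here. This stands, and it limits the point to an unsettled rule. It does not remove the need to settle it, since neither visible document says which route applies and the SAP does not repeat the Protocol's rule.

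A second reply is that the SAP worst-case analysis (9.14.1.1) already imputes inconclusive regions as FP. That is true, but it pools them with missing and non-evaluable regions, so the effect of this rule cannot be separated. The Protocol's worst-case analysis and the SAP tipping-point analysis do not name inconclusive results.

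A third reply is that the hierarchy of evidence and the next paragraph make the intended meaning of the 'or' sentence plain. That is fair for a human reader, but the sentence is still wrong as a programming rule.

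**Conclusion.** The concern holds as an unsettled classification rule in a co-primary endpoint, together with a plain wording error in Protocol 7.5.1. Under the stated assumptions, two to six equivocal-only regions move PPV from 64.7% to between 68.8% and 78.6%. Near the sizing threshold, two such regions are enough to move the lower limit across 40%. At 22 of 34 the lower limit is above 40% under either rule. The counts of equivocal-only regions are assumptions throughout.

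Three stronger readings are tempting but not supported:
- *The SAP expressly overrides the Protocol.* It does not. Exclusion is the natural reading, not a stated rule.
- *Success or failure of the trial turns on this.* SAP 4.1 plans no formal hypothesis test, and 40% is a sizing target. What is at stake is the estimate and how it is read against that target.
- *Participant-level results shift in the same way.* The Protocol's negative rule is confined to the region level, and neither document gives an equivalent rule for an equivocal-only participant, so this effect is not shown.

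**What to change.** 1. **Protocol 7.5.1:** replace 'or' with 'and', so that a region is negative only if no histopathology shows cancer and an evaluable conventional scan shows no unequivocal lesion.
2. **SAP 7.7 and 7.8, the panel charter and the programming supplement:** state that an equivocal-only region is negative in the primary analysis, as the Protocol has it. Reserve inconclusive for a documented panel judgement that the information is insufficient.
3. **SAP 9.14.1.1:** report the number of equivocal-only PET-positive regions by reader and timepoint, and region-level PPV with them excluded, as a sensitivity analysis.

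Keeping the Protocol rule as primary is preferable to adopting exclusion. It is the explicit rule, Protocol 10.1 requires the SAP to follow the Protocol's principal features, and removing regions that would otherwise be false positives can only raise PPV.

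The cost is a sentence or two in each document and one extra table, with no new data. The downside is a primary PPV less favourable than under exclusion, by the differences shown in the working. If 65% was meant for assigned regions only, power is also below the stated figure.
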